9.7.1.6.1. Adverse Events

AEs are coded using MedDRA Version 25.0. Treatment-emergent adverse events (TEAE) are defined as events that start on or after the administration of study medication and up to the earliest instance of rescue therapy. Pretreatment adverse events are events that begin prior to administration of study medication. Ocular AEs are defined as those events for which an eye has been specified (OD, OS, or OU).

Ocular and non-ocular treatment-emergent AEs will be summarized separately. Ocular AEs will be presented by study eye and non-study eye and overall (OU) if an event occurs in either eye.

In all summaries of AEs, percentages are calculated based on the number of patients in each treatment group of the Safety Analysis Set.

Overall summaries of AEs by treatment will include:

- the number of AEs and SAEs reported;
- the number and percentage of patients who experienced any AE;

- the number and percentage of patients who experienced any serious adverse event (SAE) and the reason for seriousness;
- the number and percentage of patients with any AE by worst severity and worst relationship.

The overall summaries of TEAEs will also include the number and percentage of patients with any TEAEs leading to study termination.

Summaries of the frequency and percentage of patients with AEs by SOC and preferred term by treatment group will include:

- All AEs by SOC and preferred term;
- All AEs by SOC, preferred term, and maximum severity;
- All AEs by SOC, preferred term, and maximum relationship.

System organ class (SOC) will be sorted alphabetically, and preferred term (PT) within each SOC will be sorted by overall descending order of frequency according to the following rules in order:

1. Descending frequency within AG-73305, 0.5 mg;
2. Descending frequency within AG-73305, 1 mg;
3. Descending frequency within AG-73305, 2 mg;
4. Descending frequency within AG-73305, 4 mg;
5. PT in alphabetical order.

Patients are counted only once for each SOC and PT. In summaries of maximum severity and maximum relationship, patients with multiple occurrences of events will only be counted once at the maximum severity/relationship per SOC and PT.

Any treatment-emergent AEs that have a missing severity will be presented as severe in the summary table but will be presented with a missing severity in the data listing. Any treatment-emergent AEs that have a missing relationship will be presented as “Related” in the summary table but will be presented with a missing relationship in the data listing.

All AEs are displayed in listings. In addition, separate listings will be provided for:

- Patients with any treatment-emergent adverse event leading to study termination;
- Patients with any serious adverse event (treatment-emergent or otherwise);
- Patient deaths.

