9.5.1.3.2. Secondary Efficacy Assessments

Dilated color fundus photography will be performed OU at the Baseline Visit, in the SE at Week 4, and OU at Week 24 to assess diabetic retinopathy severity score (DRSS).

Spectral Domain Optical Coherence Tomography (SD-OCT) will be performed OU at each in-clinic visit (Heidelberg Spectralis, dense scan). SD-OCT will assess central subfield thickness (CST), ellipsoid zone (EZ), external limiting membrane (ELM), intraretinal and subretinal fluid volume, and posterior vitreous detachment.

OCT Angiography (OCT-A) will be performed OU at the Baseline Visit, in the SE at Weeks 4 and 24, and OU at the visit when Rescue treatment is given. OCT-A will assess foveal avascular zone (FAZ) and foveal capillary density (CD) (superficial and deep capillary plexuses).

Color fundus photos and SD-OCT and OCT-A images will be submitted to a central reading center for grading.

Time to rescue medication will be assessed. Rescue medication will be standard-of-care anti-vascular endothelial growth factor (VEGF) administered by intravitreal injection (IVT) in the

study eye. Rescue medication is allowed at the Week 4 visit or later in patients meeting any of the criteria outlined in the protocol Section 6.5.3.

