9.7.1.1. Analysis Populations

9.7.1.1.1. Populations

The Full Analysis Set will include all patients who received at least one dose of investigational product as indicated on the dosing record. Patients will be analyzed in the group according to the treatment received. All efficacy and safety variables will be analyzed using the Full Analysis Set and only observed data will be included.

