9.7.1.4. Analysis of Study Medication Compliance and Exposure

Not applicable as this is a single dose study.

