2. ETDRS BCVA
3. Intraocular pressure (IOP)
4. Slit lamp biomicroscopy, including crystalline lens assessment using AREDS scale
5. Dilated fundus exam (DFE)
6. Post-injection assessment
7. Laboratory evaluation (hematology, serum chemistry and urinalysis)
8. Electrocardiogram (ECG)
9. Vital signs
10. Pregnancy test

The FAS will be used for all safety analyses. All data will be summarized as observed and no data imputation will be performed. No statistical treatment group comparisons will be performed, unless otherwise specified. Analyses will be presented by cohort and by study eye and non-study eye, if applicable.

Results from the physical examination performed at Screening will be presented in a listing.

All safety data will be censored (set to missing) on or after the earliest instance of rescue therapy when summarized in tables. All data will be presented in listings. This will impact the definition of TEAE.

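### AE counts stop at first rescue but AE percentages divide by everyone dosed, so cohorts whose rescue times differ are read side by side over unequal time at risk

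*SAP*

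**What the plan says.** SAP 9.7.1.6.1 defines TEAEs as "events that start on or after the administration of study medication and up to the earliest instance of rescue therapy". SAP 9.7.1.6 applies the same cut to safety tables in general: "All safety data will be censored (set to missing) on or after the earliest instance of rescue therapy when summarized in tables". It keeps all data in listings.

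For the denominator, 9.7.1.6.1 states that "percentages are calculated based on the number of patients in each treatment group of the Safety Analysis Set". The SAP does not define that set. Two other sentences indicate what is meant: "The FAS will be used for all safety analyses" (9.7.1.6) and "The Full Analysis Set will include all patients who received at least one dose of investigational product as indicated on the dosing record" (9.7.1.1.1). The divisor is therefore the number of patients dosed in the cohort.

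On timing, SAP 9.5.1.3.2 states: "Rescue medication is allowed at the Week 4 visit or later in patients meeting any of the criteria". The synopsis gives 24 weeks of follow-up after the single injection. A patient's AE window can thus be as short as about 4 weeks or as long as about 24.

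SAP 9.7.1.6 plans no statistical comparison of groups unless specified; AE results are presented by cohort.

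**The concern.** The numerator stops at a patient-specific time and the denominator does not. The percentage for a cohort is therefore the risk over whatever mix of window lengths its patients happened to have.

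Rescue closes the window, and it is triggered by loss of letters, rising CST or worsening proliferative retinopathy (synopsis). Time to rescue is itself an efficacy measure (SAP 9.7.1.5.2), and duration of effect across ascending doses is an objective (SAP 9.5.1). If doses do differ in duration of effect, AE windows will differ between the columns of the AE tables. At equal hazard, the cohort rescued later will show more patients with AEs, and one rescued early will look cleaner because counting stopped sooner.

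The plan handles this elsewhere. Time to rescue uses Kaplan-Meier with censoring, and slit-lamp and fundus percentages use patients at each visit (9.7.1.6.4, 9.7.1.6.5). The AE tables have no such adjustment. At stake is how the by-cohort AE tables are read for the objective of determining the maximum tolerated or highest administered dose.

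**Working it through.** **Figures in the plan.** No AE rate or rescue rate is stated. The only computed figures are in SAP Table 2. They reproduce as 1 − (1 − p)^n: for p = 0.3, 1 − 0.7^3 = 0.657, 1 − 0.7^6 = 0.882 and 1 − 0.7^8 = 0.942. All 24 cells agree to rounding. They do not bear on this point.

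**Inputs from the documents.** No rescue before Week 4; follow-up to Week 24; denominator = patients dosed; cohorts of 3-8.

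**Assumptions, not in the documents.** Both cohorts have the same true 24-week AE risk R. Rescue times are 4 weeks plus an exponential time, with overall median m = 8 weeks in one cohort and m = 20 in the other. There is no other dropout.

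**Mean window.** Rescue rate after Week 4: μ = ln 2/(m − 4), which is 0.1733 (m = 8) and 0.0433 (m = 20) per week. Mean window = 4 + (1 − e^(−20μ))/μ.
- m = 8: 4 + (1 − 0.0312)/0.1733 = 9.6 weeks.
- m = 20: 4 + (1 − 0.4204)/0.0433 = 17.4 weeks.

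**Planned percentage, constant hazard.** λ = −ln(1 − R)/24; for R = 0.40, λ = 0.0213 per week. With s = μ + λ, the expected percentage is

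1 − e^(−4λ) × [(μ/s)(1 − e^(−20s)) + e^(−20s)].

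| True 24-week risk | m = 8 | m = 20 |
|---|---|---|
| 20% | 8.4% | 14.7% |
| 40% | 18.0% | 30.1% |
| 60% | 29.4% | 46.5% |

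**Front-loaded events, R = 0.40.** Let a share f of events fall in week 1 and spread the rest evenly over the remaining 23 weeks. Expected percentage = 0.40f + 0.40(1 − f) × (mean window − 1)/23.
- f = 0.50: 0.20 + 0.20 × 8.59/23 = 27% versus 0.20 + 0.20 × 16.38/23 = 34%.
- f = 0.75: 0.30 + 0.10 × 8.59/23 = 34% versus 0.30 + 0.10 × 16.38/23 = 37%.
- All events before Week 4: no difference.

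**A simpler rescue pattern, R = 0.30, constant hazard.** λ = 0.01486; the risk is 11.2% by Week 8 and 16.3% by Week 12.
- 75% versus 25% rescued at Week 8: 0.75 × 0.112 + 0.25 × 0.30 = 15.9% versus 0.25 × 0.112 + 0.75 × 0.30 = 25.3%, ratio 1.59.
- Milder, 50% versus 25% rescued at Week 12: 23.2% versus 26.6%, ratio 1.15.
- Equal rescue patterns: ratio 1.00.

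**Does patient-time remove it?** In the 75% versus 25% case, expected weeks at risk to first event, rescue or Week 24 are 10.70 and 17.03 per patient. Then 0.1591/10.70 and 0.2530/17.03 both give 1.486 first events per 100 patient-weeks.

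**Size in patients.** The 12-point gap (18% versus 30%) is 0.12 × 6 = 0.7 of a patient in a cohort of 6 and 0.12 × 8 = 1.0 in a cohort of 8. The standard error of that difference with 6 per cohort is √(0.18 × 0.82/6 + 0.30 × 0.70/6) = 24 points.

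**The case against.** The strongest reply is that this matters little here. Cohorts are 3-8 patients, no tests are planned, and in the illustration chance variation is about twice the shift. Events before Week 4, including acute injection-related ones, are unaffected. Listings keep all AEs, and SAEs are listed whether or not treatment-emergent, so about 25 patients can be read individually. This all stands and limits the importance of the point. It does not remove it: chance error has no preferred direction, whereas this shift always favours the cohort rescued earlier.

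It can also be said that window length is already visible. SAP 9.7.1.5.2 plans Kaplan-Meier time to rescue and rescue use by visit, efficacy is presented by cohort, and 9.7.1.2 tabulates visit attendance. That is largely right, but none of it is joined to the AE counts.

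Three stronger readings are tempting, and the documents do not support them.
- A reader might infer that rescue time depends on dose. That is the study's question; no rescue rate by dose is given.
- A reader might take the entry in 9.7.1.4, "Not applicable as this is a single dose study", as a mistake. It concerns compliance and exposure to study medication, and for one injection given in clinic it is reasonable. Observation time is a different quantity.
- A reader might infer that the dose decision will be wrong. Cohort management is overseen by the Safety Review Committee with periodic data review (synopsis, SAP 9.7.1), and no passage available here makes final AE percentages the deciding rule.

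**Conclusion.** The point holds conditionally. The AE percentages divide events in a window closed by rescue by all patients dosed, and no planned AE output corrects for unequal windows. If time to rescue differs between cohorts, the later-rescued cohort shows a higher percentage at the same hazard.

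The size rests entirely on assumed rescue and event timing. With medians of 8 and 20 weeks and a true 40% risk, it ranges from 18% versus 30% (constant hazard) to 34% versus 37% (three quarters of events in week 1). It is zero if rescue patterns match or all events precede Week 4. In cohorts of this size that is often one patient or less. This is a reporting improvement worth making, not a flaw that invalidates the safety analysis.

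**What to change.** In SAP 9.7.1.6.1, keep the existing percentages and add for each cohort:

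1. Total patient-weeks at risk over the TEAE window, and first events per 100 patient-weeks, with each patient's time for the rate ending at the first event, first rescue or exit.
2. A supplementary AE table (patients and percent) from Day 1 to the Week 4 visit, before any rescue. This window is nearly common to all cohorts; the visit is Day 28 ± 5, so it is not exactly common. It should not replace the full-window table, because later events matter too.

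Also replace the undefined Safety Analysis Set with FAS.

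A table that simply restores post-rescue events would not do the same job. Rescued patients are assured follow-up only to Week 12 or 4 weeks after rescue, whichever is greater, so observed time could still differ, and those events follow another anti-VEGF drug.

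The cost is a few lines of SAP text and two outputs from dates already collected, with no change to conduct. The downside is that rates in cohorts of 3-8 are imprecise and assume a steady hazard, so they should be read beside the percentages and the Week 4 table.

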9.7.1.6.2. ETDRS BCVA

Descriptive summaries of the observed values at each scheduled visit as well as the change from baseline at each post-baseline visit will be presented for both eyes. Patients with a loss of ≥ 5 , ≥ 10 , and ≥ 15 letters in BCVA will be summarized by frequency and percentage.

9.7.1.6.3. Intraocular Pressure (IOP)

Descriptive summaries of the observed values at each scheduled visit as well as the change from baseline at each post-baseline visit will be presented for both eyes. Patients with an increase of ≥ 10 mmHg in IOP will be summarized by frequency and percentage.

9.7.1.6.4. Slit Lamp Biomicroscopy

The frequency and percentage of patients with observed values of each categorical response or grade as well as the categorical shift from baseline at each post-baseline visit will be tabulated at each scheduled visit for both eyes. The percentages of patients with observed values of each categorical response will be calculated based on the number of patients at each visit in each treatment group of the FAS. Percentages for categorical shifts from baseline will be based on the number of patients with baseline and post-baseline values at each visit in each treatment group.

9.7.1.6.5. Dilated Fundus Exam

The frequency and percentage of patients with observed values of each categorical response as well as the categorical shift from baseline at each post-baseline visit will be tabulated at each scheduled visit for both eyes. The percentages of patients with observed values of each categorical response will be calculated based on the number of patients at each visit in each treatment group of the FAS; percentages for vitreous hemorrhage severity and localization will be calculated based on the number of patients with vitreous hemorrhage present. Percentages for categorical shifts from baseline will be based on the number of patients with baseline and post-baseline values at each visit in each treatment group.

9.7.1.6.6. Post-Injection Assessment

The frequency and percentage of patients able to see hand motion or count fingers with the study eye will be presented.

9.7.1.6.7. Laboratory Evaluation (Hematology, Serum Chemistry and Urinalysis)

Descriptive summaries of the observed test results at Screening and Weeks 4, 12, and 24, as well as the change from baseline at Weeks 4, 12, and 24, will be presented for hematology, serum chemistry, and a subset of urinalysis labs. The frequency and percentage of patients with observed values of Low, Normal, High as well as the categorical shifts from baseline will be tabulated for hematology and serum chemistry labs. The percentages will be calculated based on the number of patients with baseline and post-baseline values at each visit in each treatment group. The frequency and percentage of patients with observed values for categorical urinalysis laboratory measurements will also be tabulated, with percentages calculated based on the number of patients with values at each visit in each treatment group.

It is expected that all samples will be analyzed by a central laboratory. If a local laboratory is used (such as for an unscheduled visit), the results will be included in the listings of laboratory data, but will not be included in descriptive summaries.

9.7.1.6.8. Electrocardiogram (ECG)

Descriptive summaries of the observed values at the Screening Visit, Visit 4, and Visit 12, as well as the change from baseline at each post-baseline visit will be presented. The frequency and percentage of patients with observed values of each categorical response as well as the categorical shift from baseline at each post-baseline visit will also be tabulated.

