Immunogenicity: Serum levels of anti-AG-73305 antibodies (using binding and neutralizing antibody assays, if available).

Study Population: Approximately 25, adult male or female patients with center involving DME in the study eye will participate in the study, including a sentinel patient in each of 4 dose cohorts.

Phase: 2a

Description of Sites: Approximately 8 sites in the United States will enroll patients.

Description of Study Treatment: AG-73305 is a humanized IgG1 Fc-fusion protein that targets vascular endothelial growth factors, placental growth factors and integrins. AG-73305 is a clear solution formulated in a 40 mg/mL concentration for intravitreal injection. Ascending doses of a single injection of AG-73305 will be assigned by cohort to 0.5, 1, 2, and 4 mg or until the maximally tolerated (or maximum administered) dose has been reached (see Table 1).

Rescue Medication will be standard-of-care anti-vascular endothelial growth factor (VEGF) administered by IVT in the study eye. Rescue medication is allowed at the Week 4 visit or later in patients meeting any of the following criteria:

- Loss of > 10 ETDRS letters from a previous best study visit with worsening of intraretinal or subretinal fluid observed by SD-OCT and judged by the Investigator to be the cause of the BCVA loss.
- Loss of > 5 ETDRS letters at 2 consecutive visits (one can be unscheduled) from a previous best study visit due to worsening of DME.
- An increase in CST > 75 μ m from a previous best study visit which remains consistently > 75 μ m from the previous best study in two consecutive visits, as assessed by SD-OCT.

The later visit can be an unscheduled visit if determined to be necessary by the Investigator.

- An increase in CST $> 50 \mu\text{m}$ from a previous best study visit, as assessed by SD-OCT and a loss of > 5 ETDRS letters, which remains consistently $> 50 \mu\text{m}$ and loss > 5 ETDRS letters from the previous best study in two consecutive visits. The later visit can be an unscheduled visit if determined to be necessary by the Investigator.
- Progression of or worsening of proliferative diabetic retinopathy.

Patients will be followed for at least 4 weeks after Rescue medication administration or through Week 12, whichever is greater.

Table 1: Summary of Open-label Cohorts and Dosing

Dose (mg)	Stock Vial Concentration (mg/mL)	Dilution Requirement	Volume to be Injected (mL)
0.5	40	1:1 with diluent	0.025
1	40	None	0.025
2	40	None	0.050
4	40	None	0.100

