2. ETDRS BCVA
3. Intraocular pressure (IOP)
4. Slit lamp biomicroscopy, including crystalline lens assessment using AREDS scale
5. Dilated fundus exam (DFE)
6. Post-injection assessment – Baseline Visit
7. Laboratory evaluation (hematology, serum chemistry and urinalysis) – Screening Visit and Weeks 4, 12, 24
8. Electrocardiogram (ECG) – Screening Visit and Weeks 4, 24
9. Vital signs
10. Pregnancy test – Baseline Visit and Week 24

A brief physical examination will also be conducted by the Principal Investigator or designee at Screening including review of systems.

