The nominal visits listed in the eCRF will be used in the summaries. In general, unscheduled visits will not be summarized in tables unless otherwise noted.

Missing Dates

Missing dates that occur for prior or concomitant medications or adverse events will be queried for a date. If no date is obtained, the following imputation rules will apply:

- For start dates, if the given year (or year-month) is the same as study drug administration, the start date will be imputed as study drug administration date; otherwise, missing month-day (or day) will be imputed as '01-01' (or '01').
- For stop dates, missing months will be imputed as '12' and missing days will be imputed as the last day of the month. If this creates a date after discontinuation/completion, the date of discontinuation/completion will be used.

Imputed dates will only be used to classify events or medications, such as occurring before or after the start of treatment. Imputed dates will only be used in tables. Listings will display the available date data.

Interim Analysis

No formal interim analysis is planned. However, as the study is open-label, safety and efficacy data will be periodically reviewed and summarized for assisting the Safety Review Committee with their assessments.

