9.7.1.3.3. Prior and Concomitant Medications

Prior and concomitant medications will be coded using the World Health Organization Drug Dictionary (WHODrug) (Version 2022-03, Lagerlund et al., 2020) for anatomical therapeutic chemical (ATC) classification and preferred drug name.

The frequency and percentage of patients with coded medications will be summarized by treatment group using the FAS. A patient who used multiple medications will be counted only once for each ATC and preferred drug name. Therapeutic Subgroup is sorted alphabetically, and preferred term is sorted by descending frequency overall within each Level 3 term according to:

1. Descending frequency within AG-73305, 0.5 mg;
2. Descending frequency within AG-73305, 1 mg;
3. Descending frequency within AG-73305, 2 mg;
4. Descending frequency within AG-73305, 4 mg;
5. PT in alphabetical order.

Prior and concomitant medications will be summarized separately. Ocular medications are defined as those medications for which an eye has been specified (OD, OS, or OU). Ocular and non-ocular medications will be summarized separately. Ocular medications will be summarized separately for study eye, non-study eye, and either eye.

Prior medications are defined as any medications that started and stopped prior to the first dose of study drug. Concomitant medications are defined as any medications that (1) start prior to the first dose of study drug and stop or are ongoing at or after the date of first dose of study drug; or (2) start at or after the first dose of study drug. Medications taken after Visit 9 or withdrawal from the study are not considered concomitant.

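### The SAP's observed-value ECG summary names a Visit 12 that does not exist, so the final scheduled ECG (Visit 9, Week 24 or Early Term) is not validly named in it

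*SAP*

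**What the plan says.** SAP 9.7.1.6.8 plans descriptive ECG summaries of "observed values at the Screening Visit, Visit 4, and Visit 12, as well as the change from baseline at each post-baseline visit". Its second sentence adds tabulation of categorical responses and their shifts from baseline.

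The places that fix which visits exist, and which carry an ECG, are:

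- **ECG schedule.** SAP 9.5.1.4, item 8, gives ECGs at "Screening Visit and Weeks 4, 24". The ECG rows in Protocol 1.3 and SAP Appendix I, Table 3, each carry three marks, matching Screening, Week 4 and the final visit.
- **Last visit.** Protocol 1.3 numbers the visits 1 to 9. SAP 9.7.1.3.3 treats Visit 9 as the end of the study: "Medications taken after Visit 9 or withdrawal from the study are not considered concomitant".
- **Visits used in tables.** SAP 9.7.1, Visit Windows: "The nominal visits listed in the eCRF will be used in the summaries", and "In general, unscheduled visits will not be summarized in tables unless otherwise noted".
- **The neighbouring laboratory section.** SAP 9.7.1.6.7 plans "Descriptive summaries of the observed test results at Screening and Weeks 4, 12, and 24". Week 12 is therefore a laboratory time point.

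On ECG content, SAP 9.5.1.4.8 lists QT and RR among the measures assessed. No rate-corrected QT appears in the available text of either document.

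**The concern.** An analysis section should tell the programmer which visits go into a table. Here one of the three named visits does not exist, and the one left out is the last ECG of the study. Followed literally, the change-from-baseline table would show Week 24 with no matching row of observed values. Someone correcting the label without guidance could choose Week 12 (from the number) or Week 24 (from the ECG schedule).

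A smaller matter sits in the same section. Raw QT shortens as heart rate rises and lengthens as it falls. If raw QT is the only QT measure summarised, its change from baseline cannot be read as a change in repolarisation alone.

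**Working it through.** **Visit label.** The documents give no computed figure to reproduce here. The check sets the visits named in SAP 9.7.1.6.8 against the visit numbering and the ECG schedule.

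| Visit | Time point | ECG scheduled? | Named in the observed-value list? |
|---|---|---|---|
| 1 | Screening | Yes | Yes |
| 4 | Week 4 | Yes | Yes |
| 6 | Week 12 | No | Only if Visit 12 is read as Week 12 |
| 9 | Week 24 or Early Term | Yes | No |
| 12 | Does not exist | – | Yes |

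The remaining visits (2 Baseline, 3 Week 1, 5 Week 8, 7 Week 16, 8 Week 20) carry no scheduled ECG.

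The possible readings of Visit 12 are:

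1. *A visit number.* Numbering stops at 9. The header of SAP Table 3 is garbled in the extracted text, but even counting the next-day follow-up as a separate column there are only 10 columns.
2. *Week 12.* This is Visit 6, which has laboratory tests but no ECG.
3. *An unscheduled visit.* The Visit Windows rule generally keeps these out of tables.

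Coverage of the three scheduled ECG time points in the observed-value list:

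- as written: Visits 1 and 4, so 2 of 3;
- read as Week 12: still 2 of 3;
- with Visit 9 substituted: 3 of 3.

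The other outputs for Week 24 were then checked. Change from baseline and categorical shifts are planned for every visit after baseline, which includes Visit 9. SAP 9.7.1, General Conventions, puts all collected data in patient listings. The gap is therefore one row of observed values in a descriptive table. SAP 9.7.1.6 separately states: "All safety data will be censored (set to missing) on or after the earliest instance of rescue therapy when summarized in tables". That rule can remove Week 24 values from the tables whatever the visit is called, so it does not measure this defect.

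**Rate-corrected QT.** Fridericia's formula is QTcF = QT / RR^(1/3), with RR in seconds, or equivalently QT = QTcF × (60/HR)^(1/3). All inputs below are assumptions, not figures from the documents.

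- Hold QTcF at 400 ms. At 70 bpm, QT = 400 × (60/70)^(1/3) = 380.0 ms. At 80 bpm, QT = 400 × (60/80)^(1/3) = 363.4 ms. Raw QT moves by about −16.5 ms with no change in QTcF.
- Over QTcF of 400 to 440 ms and shifts of 5 to 15 bpm from 70 bpm, raw QT changes by −8.6 to −26.2 ms when the rate rises and by +9.5 to +35.0 ms when it falls.

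This shows only that raw QT follows heart rate. It does not predict any effect in this trial.

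**The case against.** The strongest case is that the label is a slip that nearly corrects itself. The SAP states the ECG schedule plainly in 9.5.1.4, tables use the nominal eCRF visits, and only three of those carry a scheduled ECG. A programmer would probably reach Week 24. The second sentence of 9.7.1.6.8 also tabulates categorical ECG responses, and its reference to every visit after baseline can be read as covering the observed categories too. All of this stands, and it is why the point is minor. It does not make the sentence right: no reading of Visit 12 matches a scheduled ECG.

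A reader might infer that the Week 24 ECG goes unanalysed. The documents do not support that, since change from baseline, categorical shifts and listings all reach it.

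On QTc, the objection is that nothing in the documents is contradicted and no data are lost, because a correction could be programmed from stored QT and RR at any time. That also stands. A reader might further infer that the trial has no QTc rule, or that the SAP commits to separate QT and RR tables. Neither can be established. Most of the protocol body is not in the public text, the SAP sends all ECGs to a central reader whose specification is not available, and 9.7.1.6.8 does not name the parameters to be summarised. The QTc suggestion is therefore an optional improvement, not an error in the plan.

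**Conclusion.** The visit label is wrong as written, with high confidence. One of the three scheduled ECG time points, Visit 9 (Week 24 or Early Term), has no valid entry in the observed-value summary. Severity is minor. ECG is one of ten descriptive safety items, no statistical comparison between groups is planned unless otherwise specified, and neither the sample size nor the primary efficacy endpoint is touched. The conclusion rests only on the visit numbering and ECG schedule stated in the two documents.

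The QTc suggestion carries moderate confidence. It assumes that QT and RR are recorded as numbers for each tracing, as the list in SAP 9.5.1.4.8 implies, and that no QTc rule exists in text not available here.

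**What to change.** 1. In SAP 9.7.1.6.8, replace Visit 12 with Visit 9 (Week 24 or Early Term). Naming the other two as Visit 1 (Screening) and Visit 4 (Week 4) would remove any remaining confusion between visit and week numbers. This is a text correction only.
2. Optional: add a sentence to the same section stating that QTcF = QT / RR^(1/3), with RR in seconds, will be derived for each tracing and that observed values and change from baseline will be summarised beside raw QT. If the full protocol or the central reader already defines a QTc, name that one instead. The cost is one sentence and at most one derived variable.

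Neither change needs new data, visits or procedures.
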